8. STUDY CALENDAR

Baseline evaluations are to be conducted within 2 weeks prior to administration of protocol therapy. Scans and x-rays must be done ≤4 weeks prior to the start of therapy. In the event that the patient's condition is deteriorating, laboratory evaluations should be repeated within 48 hours prior to initiation of the next cycle of therapy.

	-28 days	-14 days (may serve as cycle 1 day 1 labs)	Day 1 (± 1 day) of every cycle (28 days)	Day 8 and 15 every cycle (± 1 day)	Day 1 Every 3 cycles	30 (± 7 days) post last treatment
ASSESSMENTS						
History and exam (H&P)	X		X			X ¹
ECOG performance status		X	X			X ¹
CBC with differential		X	X	X		X ¹
CMP		X	X			X ¹
PSA		X	X			X ¹
LDH		X				
Testosterone level		X				
Pain (PPI 0-5 scale)		X	X			X ¹
Analgesic intake (increased, decreased or stable)		X	X			X ¹
Echocardiogram	X		X ^{6,7}			
DISEASE ASSESSMENT						

CT chest , abdomen, pelvis	X				X	X ¹
Bone Scan	X				X	X ¹
TREATMENT						
Carfilzomib day 1,2, 8,9,15,16 (30 min IV infusion)			X ²	X ²		
Premedication (Dexamethasone, Acetaminophen)			X ³	X ³		
Pre-hydration (Normal saline 250-500 ml over 30 minutes)			X ⁴	X ⁴		
Acyclovir 400 mg PO bid			X ⁵	X ⁵		
LHRH analogue (if no prior orchiectomy)					X	
CORRELATIVE STUDIES						
CTC enumeration (3 time points)	X		X (cycle 2 only)		X (cycle 4 only)	
Whole Blood 20S proteasome assay	X					
FOLLOW-UP						
Disease progression and survival						X ¹

¹Patients removed from trial for reasons other than progression will continue to be followed until progression or initiation of new therapy (whichever comes first); i.e. H&P, laboratory evaluation, pain, analgesic intake are performed every ~28 days and radiographic evaluation every ~90 days (+/-7 days); ²Dose is 20 mg/m² on days 1, 2 of cycle 1 and if no DLTs, escalate to 56 mg/m² for all remaining doses, Subjects with a Body Surface Area (BSA) > 2.2 m² will receive a capped dose of 44 mg of carfilzomib (at the 20 mg/m² dose level) or 123 mg of carfilzomib (at the 56 mg/m² dose level); ³Dexamethasone dose is 4 mg PO/IV with carfilzomib 20 mg/m² and 8 mg PO/IV with carfilzomib 56 mg/m², dexamethasone may be discontinued from cycle 2 day 1 if patient is tolerating carfilzomib therapy per investigator discretion and/or has adverse effects from dexamethasone, acetaminophen dose is 650 mg PO x 1; ⁴Prehydration with 250-500 ml of normal saline is given during cycle 1 and may be discontinued from cycle 2 day1 per investigator discretion (post-hydration with 250-500 ml normal saline is optional per investigator discretion); ⁵Acyclovir to start on day 1 of cycle 1 and stop ≥7 days after last dose of carfilzomib; ⁶Only if clinically indicated for patients who develop CHF on study; ⁷Multigated Acquisition Scan (MUGA) is acceptable

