Study drug should be held for \geq Grade 3 events until resolved to \leq Grade 1 or return to baseline. After resolution of the event to \leq Grade 1 or return to baseline, if the adverse event was not treatment-related, subsequent treatment with carfilzomib may resume at full dose. If the event was treatment-related, subsequent treatment with carfilzomib will resume at one level dose reduction. If toxicity continues or recurs, further carfilzomib dose reduction may be permitted at the discretion of the investigator. If toxicity continues to recur after dose reduction to 15 mg/m², the subject should be removed from study. If there is no resolution of toxicity after 3 weeks of withholding treatment, the subject will be withdrawn from the study.

Dose adjustment guidelines for non-hematologic toxicities are summarized as follows:

Symptom	Recommended Action
	Carfilzomib
Allergic reaction/hypersensitivity	
Grade 2 – 3	Hold until \leq Grade 1, reinstitute at full dose.
Grade 4	Discontinue
Tumor lysis syndrome (≥ 3 of following: $\geq 50\%$ increase in creatinine, uric acid, or phosphate; $\geq 30\%$ increase in potassium; $\geq 20\%$ decrease in calcium; or ≥ 2 -fold increase in LDH)	Hold carfilzomib until all abnormalities in serum chemistries have resolved. Reinstitute at full doses.
Infection Grade 3 or 4	Hold carfilzomib until systemic treatment for infection complete. If no neutropenia, restart at full dose. If neutropenic, follow neutropenic instructions.
Herpes zoster or simplex of any grade	Hold carfilzomib until lesions are dry. Reinstitute at full dose
Gr 2 treatment emergent neuropathy with pain	Continue to dose. If neuropathy persists for more than two weeks hold carfilzomib until resolved to \leq Gr 2 without pain. Then restart at 1 dose decrement

Grade \geq 3 neuropathy	Discontinue
Renal Dysfunction	
CrCl <30 mL/min	Hold until CrCl \geq 30 mL/minute; restart at 1 dose decrement
Congestive heart failure	Any subject with symptoms of congestive heart failure, whether or not drug related, must have the dose held until resolution or return to baseline, after which treatment may continue at a reduced dose, or the subject may be withdrawn from the study. If no resolution after 2 weeks, the subject will be withdrawn from the study.
Other non-hematologic toxicity assessed as carfilzomib-related \geq Grade 3	Hold dose until toxicity resolves to \leq Grade 1 or baseline. Restart at 1 dose decrement.

Increased Creatinine or Decreased CrCl

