Modest activity is considered clinically meaningful in this relatively heavily pretreated population with metastatic CRPC that has received abiraterone acetate and/or enzalutamide (prior chemotherapy and sipuleucel-T are allowed). The null hypothesis for this trial is that the primary endpoint of 6-month PFS <10% is not clinically meaningful and the alternative hypothesis is that the true clinical PFS of interest is $\geq 30\%$. Since we will follow all subjects for at least 6 months or until progression or death, we will not have censoring and 6 months PFS can be treated as a binomial random variable. With twenty five evaluable patients we will have 80% power for an exact binomial test at the one sided 0.05 significance level of the null hypothesis that the 6-month PFS rate is 10% if the actual rate is 30%. That null hypothesis will be rejected if 6 or more of the 25 subjects survive for 6 months progression free. Twenty-eight subjects will be accrued to allow for 10% inevaluable patients.

Sample Size/Accrual Rate

A total of 28 patients will be enrolled for this trial. Accrual period will be 6 to 12 months.

Analysis of Secondary Endpoints

The Kaplan-Meier method will be used to estimate PFS and OS rates over time with standard errors estimated using Greenwood's formula. Medians and their 95% confidence intervals will also be estimated. PSA response, PSA decline $\geq 30\%$ within 3 months, RECIST responses and regressions, pain response and CTC alterations will be analyzed as secondary endpoints. CTC changes will include changes from unfavorable ($\leq 5/7.5\text{ml}$) to favorable, and declines by $>30\%$. Pain response is defined as decline in present pain index ≥ 2 points and/or decrease in analgesics. Linear regression with PSA as the dependent variable and time as the dependent variable will be performed and used to estimate PSA DT. The association of baseline whole blood 20S proteasome level with PFS and other secondary endpoints will be examined using Cox regression to generate hypotheses for selecting suitable patients for further study.

Reporting and Exclusions

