11. MEASUREMENT OF EFFECT

Antitumor Effect

For the purposes of this study, patients should be re-evaluated for response every 12 weeks and earlier if clinically required. Response and progression will be evaluated in this study using the new international criteria proposed by the Response Evaluation Criteria in Solid Tumors (RECIST 1.1)[26]. Changes in only the largest diameter (unidimensional measurement) of the tumor lesions are used in the RECIST criteria.

All patients will be evaluable for toxicity from the time of their first treatment with Carfilzomib. Only those patients who have measurable disease present at baseline, have received at least one cycle of therapy, and have had their disease re-evaluated will be considered evaluable for response. These patients will have their response classified according to the definitions stated below. (Note: Patients who exhibit objective disease progression prior to the end of cycle 1 will also be considered evaluable.)

Measurable disease. Measurable lesions are defined as those that can be accurately measured in at least one dimension (longest diameter to be recorded) as ≥ 20 mm with conventional techniques (CT, MRI, x-ray) or as ≥ 10 mm with spiral CT scan. Lymph nodes are considered measurable if the short axis diameter is ≥ 15 mm. All tumor measurements must be recorded in millimeters (or decimal fractions of centimeters). Tumor lesions that are situated in a previously irradiated area might or might not be considered measurable

Non-measurable disease. All other lesions (or sites of disease), including small lesions (longest diameter < 20 mm with conventional techniques or < 10 mm using spiral CT scan), are considered non-measurable disease. Bone lesions, leptomeningeal disease, ascites, pleural/pericardial effusions, lymphangitis cutis/pulmonis, inflammatory breast disease, abdominal masses (not followed by CT or MRI), and cystic lesions are all non-measurable.

Bone disease: According to PCWG-2 guidelines, 2 distinct new lesions on bone scan consistent with bone metastases in the best judgment of the investigator and confirmed by further new lesions on a subsequent scan ≥ 6 weeks later is defined as bone scan progression.

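### CT and bone scans follow cycle number, so dosing delays of more than about two weeks can move the second scan past 6 months and hide imaging-only progression from the primary endpoint

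*Combined protocol and SAP*

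**What the plan says.** Imaging frequency is stated in three ways.

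- **On treatment, by cycle.** The Study Calendar (Section 8 and Synopsis) puts CT and bone scan under "Day 1 Every 3 cycles". The Synopsis, Section 3.1 and Section 6.3 also give every 3 cycles, or earlier if clinically indicated. The same calendar column holds the cycle 4 CTC sample, so the scans fall on day 1 of cycles 4, 7 and 10.
- **By calendar time.** Section 11 says that "patients should be re-evaluated for response every 12 weeks and earlier if clinically required".
- **Off treatment without progression.** Footnote 1 of the calendar gives "radiographic evaluation every ~90 days", with a 7-day window either side.

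Cycles last 28 days, with a 1-day window on Day 1. Section 7 allows treatment to be held for toxicity and sets the limit for withdrawal as follows: "If there is no resolution of toxicity after 3 weeks of withholding treatment". It also says that missed doses are not made up within a cycle.

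Section 11 starts the PFS clock at the start of treatment. Section 10 treats 6-month PFS as a binomial outcome without censoring and states: "That null hypothesis will be rejected if 6 or more of the 25 subjects survive for 6 months progression free". The documents do not give:

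- 6 months in days;
- a window for the landmark scan;
- a rule on whether a hold moves the scan;
- a rule for progression first seen on a scan shortly after 6 months.

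**The concern.** A binomial analysis without censoring needs each patient's status to be known at the landmark. For the two imaging components of progression (RECIST and bone scan), status is known only as of the last scan before 6 months. If scans follow cycle number, the timing of that scan depends on dosing delays, which vary between patients and reflect tolerability.

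The error has a direction. A scan that slips past 6 months cannot create a false failure at the landmark, but it can leave a progressor looking progression-free. In a single-arm trial decided on 6 of 25 patients, one such case can change the conclusion.

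**Working it through.** **1. The plan's own figure.** The inputs are in Section 10: "With twenty five evaluable patients we will have 80% power for an exact binomial test at the one sided 0.05 significance level", with rates of 10% and 30% and rejection at 6 or more.

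- Size: P(X ≥ 6 | n = 25, p = 0.10) = 0.0334.
- Power: P(X ≥ 6 | n = 25, p = 0.30) = 0.8065.
- Accrual: 25 / 0.9 = 27.8, so 28.

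The stated 80% power and 28 patients are reproduced. The attained size is 0.033 against a nominal 0.05.

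**2. Scan dates without delay.** Day = (cycle − 1) × 28 + 1.

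- Cycle 4: day 85 (84 days elapsed).
- Cycle 7: day 169 (168 days elapsed).
- Cycle 10: day 253 (252 days elapsed).

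**3. Slack before the landmark.** This is 6 months in days minus 168.

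- 180 days: 12
- 182 days (26 weeks): 14
- 182.6 days: 14.6
- 184 days: 16
- 168 days (24 weeks): 0

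The 1-day visit window cannot use up two weeks. A hold of up to 3 weeks, or several shorter ones, can do so if it moves Day 1.

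**4. Effect of one misclassified progressor.** A trial with exactly 5 true successes would then reject. The rule acts like 5 of 25: size 0.0334 + P(X = 5) = 0.0334 + 0.0646 = 0.0980.

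**5. Effect of delay alone.** The assumptions, none of them from the documents, are:

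- PFS is exponential with a true 6-month rate of 10%, so S(t) = 0.10^(t/182.625).
- A share f of progressions is visible only on imaging.
- A share d of patients has the second scan after 6 months, independently of progression.
- Imaging-only progression is dated at the scan that shows it, and no earlier scan is triggered.

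S(84) = 0.3468 and S(168) = 0.1202, so 22.65% of patients progress between the two scheduled scans. Relative to an undelayed schedule, delay adds 0.2265 × f × d to the rate counted as success:

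| f | d | Counted rate | Expected false successes in 25 | Size |
|---|---|---|---|---|
| – | 0 | 10.0% | 0 | 0.033 |
| 0.25 | 0.10 | 10.6% | 0.14 | 0.042 |
| 0.50 | 0.10 | 11.1% | 0.28 | 0.052 |
| 0.50 | 0.25 | 12.8% | 0.71 | 0.092 |

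Expected false successes are 25 × 0.2265 × f × d. The size passes 0.05 when f × d is a little under 0.05.

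**6. A separate effect without delay.** A punctual day-169 scan still misses imaging-only progression in the last two weeks. In the same model this gives a counted rate of 11.0% and size 0.050 at f = 0.5, and 12.0% and about 0.07 at f = 1. This is ordinary interval detection and is left out of the table.

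**7. Bone scans.** Confirmation is required at least 6 weeks later. New lesions seen on day 169 are therefore confirmed on day 169 + 42 = 211 at the earliest, after the landmark even with no delay. The plan does not say which date counts.

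**The case against.** Several points on the other side stand.

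- **Imaging is not tied to cycles throughout.** Section 11's 12-week interval, read literally, would not move with a dose delay, and off-treatment imaging already follows the calendar. The finding is therefore a conflict between passages, with nothing to say which governs.
- **Most of the endpoint does not wait for a scan.** Pain, analgesic use and performance status are recorded every cycle. Obstruction, skeletal events and death count when they occur. A scan may also be brought forward on clinical grounds. A reader might infer that 6-month status as a whole is read at day 169, but only its imaging part is.
- **Not every hold moves Day 1.** Missed doses are not replaced, so a hold within a cycle may leave cycle 7 day 1 where it was. A patient withdrawn after 3 weeks without resolution passes to calendar imaging. A reader might infer that any two-week delay turns a progressor into a success. That also requires the progression to be imaging-only, to arise after day 85 and to prompt no earlier scan.
- **The plan does not say that a late scan is ignored.** A reader might infer that such a patient counts as progression-free whatever the scan shows. The documents are silent, and that silence is the gap.
- **f and d are assumed.** At the low end the size stays below 0.05. Adding the interval-detection effect of step 6 would give larger figures, but they could not be attributed to delay.

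What remains is that the calendar and three text sections give the cycle-based rule, the slack is about two weeks, and no rule covers a late scan.

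**Conclusion.** The concern holds in a limited form. The imaging rules conflict once a cycle is delayed. Under the cycle-based one, accumulated delays of more than about two weeks leave the day-85 scan as the only one before 6 months. The resulting error affects imaging-only progression arising after day 85, and it favours success.

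The size of the effect is uncertain. Delay alone moves the false-positive rate from 0.033 to between 0.042 and 0.092 over the assumed values, and only the first of the three scenarios stays within 0.05. The firmer result is the sensitivity of the rule, since a single misclassified progressor corresponds to a size of 0.098. That rests only on the plan's own n, null rate and cut-off.

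**What to change.** 1. Reconcile the Synopsis, Sections 3.1, 6.3 and 8 (with footnote 1) and Section 11. Schedule CT and bone scans in calendar time from cycle 1 day 1, on and off treatment, regardless of dose delays.
2. Define 6 months in days. Place the second scan at that landmark, or in a stated window ending there. The window should be short, because step 6 shows that a scan two weeks early still misses some progression. In the model of step 5, a scan at the landmark restores size 0.033 and power 0.807.
3. Keep the 6-month endpoint, the 10% null and the 6-of-25 rule. Do not redefine the endpoint as status at week 24 unless the null is restated. Under the same model a true 6-month rate of 10% corresponds to 12.0% at 24 weeks, and an unchanged rule would then have size of about 0.07.
4. If the landmark scan is missed or late and the first later scan shows progression, count the patient as not progression-free at 6 months.
5. Date bone-scan progression that is confirmed at least 6 weeks later to the first scan showing the new lesions.

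The cost is wording in the calendar, the text and the statistical section; no additional scheduled scans are needed. The late-scan rule is slightly conservative, because some progression that truly began after 6 months will count as failure.

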9. ADVERSE EVENTS: LIST AND REPORTING REQUIREMENTS

Adverse event (AE) monitoring and reporting is a routine part of every clinical trial.

Serious Adverse Events (SAEs) are reported by the site Lead Investigator within 24 hours to the Clinical Trial Network Monitoring Office (CTNMO) Coordinating Center Manager

by email ([contact]) or by [contact]. The 24 hour paging number for the CTNMO Coordinating Center Manager is [contact], [name]. The CTNMO Manager is then responsible for reporting SAEs to the UAB IRB and protocol P.I. in accordance with study-specific requirements. SAEs occurring at CTNMO sites are reported to the UAB IRB as “non-UAB” events.

A Serious Adverse Event (SAE) is an AE that 1) results in patient hospitalization or prolongation of hospitalization; 2) results in persistent or significant disability or incapacity; 3) results in death; 4) is a cancer or congenital abnormality or 5) results in the development of drug dependence or abuse. An AE must be considered an SAE when the nature or severity of the event is not consistent with the current Investigator’s Brochure. CTNMO site SAEs must be reported by the CTNMO site Lead Investigator to the CTNMO Coordinating Center Manager by email or by fax. It is also the responsibility of the CTNMO site Lead Investigator to report SAEs to the CTNMO site IRB and to submit copies of that report to the CTNMO Coordinating Center Manager. It is the CTNMO Coordinating Center Manager’s responsibility to report the SAE to the appropriate regulatory agency and / or industry sponsor. This submission of IND Safety Reports will be cross referenced according to local regulations to Onyx Investigational Compound Number (IND) at the time of submission.

Comprehensive Adverse Events and Potential Risks List (CAEPR)

The Comprehensive Adverse Event and Potential Risks list (CAEPR) provides a single, complete list of reported and/or potential adverse events (AE) associated with an agent using a uniform presentation of events by body system. In addition to the comprehensive list, a subset, the Agent Specific Adverse Event List (ASAEL), appears in a separate column and is identified with bold and italicized text. This subset of AEs (the ASAEL) contains events that are considered ‘expected’ for expedited reporting purposes only. The CAEPR may not provide frequency data; if not, refer to the Investigator’s Brochure for this information.

Adverse Event Characteristics

- CTCAE term (AE description) and grade: The descriptions and grading scales found in the revised NCI Common Terminology Criteria for Adverse Events (CTCAE) version 4.03 will be utilized for AE reporting. All appropriate treatment areas should have access to a copy of the CTCAE version 4.03.
- “Expectedness”: AEs can be ‘Unexpected’ or ‘Expected’ for expedited reporting purposes only. ‘Expected’ AEs (the ASAEL) are bold and italicized in the CAEPR.
- Attribution of the AE:
 - Definite – The AE *is clearly related* to the study treatment.
 - Probable – The AE *is likely related* to the study treatment.
 - Possible – The AE *may be related* to the study treatment.
 - Unlikely – The AE *is doubtfully related* to the study treatment.
 - Unrelated – The AE *is clearly NOT related* to the study treatment.

Expedited Adverse Event Reporting

Expedited AE reporting for this study must use the reporting procedures briefly outlined in the table below.

Expedited Reporting Guidelines – Reporting Requirements for Adverse Events that occur within 30 Days¹ of the Last dose of the Investigational Agent on Phase 2 and 3 Trials

	Grade 1	Grade 2	Grade 2	Grade 3		Grade 3		Grades 4 & 5 ²	Grades 4 & 5 ²
	Un-expected and Expected	Unexpected	Expected	Unexpected with Hospitalization	without Hospitalization	Expected with Hospitalization	without Hospitalization	Unexpected	Expected
Unrelated Unlikely	Not Required	Not Required	Not Required	10 Calendar Days	Not Required	10 Calendar Days	Not Required	10 Calendar Days	10 Calendar Days
Possible Probable Definite	Not Required	10 Calendar Days	Not Required	10 Calendar Days	10 Calendar Days	10 Calendar Days	Not Required	24-Hour; 5 Calendar Days	10 Calendar Days

¹ Adverse events with attribution of possible, probable, or definite that occur greater than 30 days after the last dose of treatment require reporting as follows:

24-hour notification followed by complete report within 5 calendar days for:

- Grade 4 and Grade 5 unexpected events

10 calendar day report:

- Grade 3 unexpected events with hospitalization or prolongation of hospitalization
- Grade 5 expected events

² Although a 24-hour notification is not required for death clearly related to progressive disease, a full report is required as outlined in the table.

Note: All deaths on study require both routine and expedited reporting regardless of causality. Attribution to treatment or other cause must be provided.

- Expedited AE reporting timelines defined:
 - “24 hours; 5 calendar days” – The investigator must initially report the AE within 24 hours of learning of the event followed by a complete report within 5 calendar days of the initial 24-hour report.
 - “10 calendar days” - A complete report on the AE must be submitted within 10 calendar days of the investigator learning of the event.
- Any medical event equivalent to CTCAE grade 3, 4, or 5 that precipitates hospitalization (or prolongation of existing hospitalization) must be reported regardless of attribution and designation as expected or unexpected with the exception of any events identified as protocol-specific expedited adverse event reporting exclusions.
- Any event that results in persistent or significant disabilities/incapacities, congenital anomalies, or birth defects must be reported.
- Use the protocol number and the protocol-specific patient ID assigned during trial registration on all reports.

Expedited Reporting by Investigator to Onyx

The Investigator must inform Onyx in writing by e-mail or Fax at the contact information listed below of all Expedited Safety Reports submitted to the relevant health authorities (HA). **These notifications should be performed in parallel to the HA submissions [e.g., within 7 calendar days for any fatal or life-threatening suspected unexpected serious adverse reactions (SUSARs) and within 15 calendar days for all other SUSARs}, but in no case any later than 1 business day from the submission date. This must be documented on a FDA 3500a MEDWATCH or CIOMS I form. All other SAEs will be sent to Onyx within 30 days of the event on a FDA 3500a MEDWATCH, CIOMS I, or local SAE form. All forms must be completed and provided to Onyx in English.**

The initial report must be as complete as possible, at a minimum including the SAE term(s), patient identifier, date of awareness of the event, an investigator assessment of the causal relationship between the event and the Onyx product(s), and name of the investigator. Information not available at the time of the initial report (e.g., an end date for the SAE or laboratory values received after the report) must be documented on a follow-up form, and submitted to Onyx in the same timelines as outlined above. The Onyx protocol number (IST-CAR-612) and the institutional protocol number should be included on all SAE reports to Onyx.

All other SAE's will be sent to Onyx on a biannual basis in the form of a line listing in English. The line listing must include the following information; patient initials, date of birth, sex, SAE onset date, SAE stop date, event name (term), outcome, date of first dose of study drug(s), date of last dose of study drug(s) prior to the event, action taken with study drug(s) the Investigator's assessment of causality (relationship to carfilzomib), and the Investigator's assessment of expectedness to carfilzomib. The sponsor reserves the right to review the CRFs or source documents in response to any inquiries by regulatory agencies that the sponsor may receive.

Onyx Drug Safety and Pharmacovigilance Contact Information:

Drug Safety Reporting Email: [contact]

Drug Safety Reporting [contact] (toll fax) or 1 [contact] (US toll-free fax)

Pregnancy Reporting by Investigator-sponsor to Onyx

If a subject or partner of a subject becomes pregnant during treatment with an Onyx product(s) or up to 30 days following the last dose of an Onyx product(s), the Investigator-sponsor will notify Onyx within 24 hours of learning of the pregnancy. The investigator will complete a local Pregnancy Monitoring Form and report the information regarding the pregnancy, outcome, and status of the newborn, to Onyx via the contact information above as appropriate.

If the subject becomes pregnant while taking an Onyx product(s), the drug will be immediately discontinued. The investigator will discuss the risks and concerns of investigational drug exposure to a developing fetus and counsel the subject and/or pregnant partner (or ensure that such counseling is provided). Pregnancies will be followed through the outcome of the pregnancy. Newborns should be followed for a minimum of 12 weeks.

Routine Adverse Event Reporting

All Adverse Events **must** be reported in routine study data submissions. AEs reported must also be reported in routine study data submissions. Safety will be monitored throughout the study by physical examinations, review of adverse events (AEs), and laboratory studies. The frequency of safety monitoring procedures is outlined in Section 7. Criteria that will be used throughout the study for dose interruption, reduction, and discontinuation of chemotherapeutic agents are specified in Section 7. The frequency of efficacy monitoring and procedures are outlined in Sections 8.

Data and Safety Monitoring Plan

Subjects treated at UAB will be monitored by the UAB Comprehensive Cancer Center Data and Safety Monitoring Plan (DSMP). Adverse reactions observed during treatment will be closely monitored by the Clinical Trials Monitoring Committee (CTMC) on a weekly basis. The CTMC is responsible for data and safety monitoring of the trial and adherence to the DSMP. The independent Quality Assurance Committee (QAC) is responsible for oversight of the operation of CTMC, including adherence to the DSMP. Reports from the CTMC are reviewed monthly by the QAC.

Protocol Management and Oversight of Participating Outside Sites

[name] functions as the sponsor of the trial at UAB and at the outside sites. The outside sites will utilize their respective IRB of record. The Principal Investigator at the outside sites will be responsible for ensuring that all the required data will be collected and entered onto the Case Report Forms. Periodically, monitoring visits will be conducted and the Principal Investigator will provide access to his/her original records to permit verification of proper data entry. At the completion of the study, all case report forms will be reviewed by the Principal Investigator and will require his/her final signature to verify the accuracy of the data

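### The SAE definition in Section 9 leaves out life-threatening events, so an expected one without hospitalization, disability or death is not an SAE and misses 24-hour reporting

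*Combined protocol and SAP*

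**What the plan says.** All the text is in Section 9 of the protocol.

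- **Deadline.** "Serious Adverse Events (SAEs) are reported by the site Lead Investigator within 24 hours" to the coordinating center manager, who passes them to the UAB IRB and the protocol principal investigator.
- **Definition.** There are five numbered criteria. The first is in "A Serious Adverse Event (SAE) is an AE that 1) results in patient hospitalization or prolongation of hospitalization". The second is that the event "results in persistent or significant disability or incapacity". The rest read "results in death; 4) is a cancer or congenital abnormality or 5) results in the development of drug dependence or abuse".
- **Extra trigger.** Straight after the list: "An AE must be considered an SAE when the nature or severity of the event is not consistent with the current" Investigator's Brochure.
- **Expedited table.** For Grade 4 and 5 events within 30 days of the last dose, only the unexpected and related cell requires 24-hour notice (full report within 5 calendar days). The other three cells have 10 calendar days. A footnote covers related events later than 30 days.
- **Reporting to the company.** A 7-calendar-day clock applies to "any fatal or life-threatening suspected unexpected serious adverse reactions".

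**The concern.** The company-reporting text treats life-threatening as a class of seriousness, but the definition that starts the 24-hour duty does not contain it. The list is numbered one to five and complete, and nothing elsewhere in the document adds the criterion. A site that follows the definition exactly will therefore classify some life-threatening events as non-serious.

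SAE status decides more than the first 24-hour report. In Section 9 it also governs:
- reports to the UAB IRB, the protocol principal investigator and the site's own IRB;
- reports to the regulatory agency or the company;
- the individual SAE forms due to the company within 30 days;
- the twice-yearly SAE line listing to the company.

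The setting makes such events plausible. Treatment is given to outpatients (Section 6.1). Section 7 itself provides for Grade 4 hypersensitivity, Grade 4 thrombocytopenia with bleeding, tumor lysis, and a first-dose reaction for which vasopressors and oxygen are to be at hand.

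**Working it through.** The plan gives no figure to reproduce and no formula applies. The check follows one event through the rules: life-threatening, with no hospitalization, disability or death, and meeting none of the other numbered criteria.

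Two readings are needed. Grade 4 is taken as life-threatening, because Appendix D only links to CTCAE v4.03 and does not define the grades. Inconsistent with the Brochure is taken as unexpected, although Section 9 elsewhere ties expectedness to the agent-specific adverse event list.

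**Within 30 days of the last dose**

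| Case | SAE by the five criteria? | SAE by the Brochure sentence? | Expedited table, Grade 4 | Shortest deadline |
|---|---|---|---|---|
| Unexpected, related | No | Yes | 24 hours, full report in 5 days | 24 hours |
| Unexpected, unrelated or unlikely | No | Yes | 10 calendar days | 24 hours, as an SAE |
| Expected, related | No | No | 10 calendar days | 10 calendar days |
| Expected, unrelated or unlikely | No | No | 10 calendar days | 10 calendar days |

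Two of the four cases fall outside 24-hour reporting, and both are expected events. If both clocks start when the investigator learns of the event, the permitted delay is 10 − 1 = 9 days longer.

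**More than 30 days after the last dose, related.** The footnote's 24-hour list holds unexpected Grade 4 and 5 events. Its 10-day list holds unexpected Grade 3 events with hospitalization, and expected Grade 5 events. An expected Grade 4 event is on neither list.

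**Other rules that might close the gap.** The bullet that requires reporting of Grade 3 to 5 events whatever their attribution or expectedness applies only if the event leads to or prolongs hospitalization. The bullet on disability and birth defects does not apply to this event either.

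**The 7-day clock.** It concerns unexpected reactions only. The Brochure sentence already makes those SAEs, so that stream is not the one left open.

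**The case against.** A reader might infer that every life-threatening event managed without hospitalization escapes 24-hour reporting. The documents do not support that. The Brochure sentence carries no hospitalization condition, so an unexpected event is an SAE whether or not it is related to treatment, and the table separately gives 24-hour notice when it is also related. The apparent clash with the 7-day clock largely disappears for the same reason.

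A reader might also infer that the weekly monitoring committee would learn of these events late. That is not supported either. Under the monitoring plan in Section 9 the committee follows adverse reactions weekly. Under the multicenter guidelines in Section 14 each subject is discussed at the site's weekly meeting and presented at the next weekly central meeting by the coordinating center manager. Neither route depends on SAE status. Section 7 requires a toxicity check before each dose, and Section 9 requires all adverse events in routine data submissions. The event is therefore not lost from view.

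Finally, the 10-day figure depends on equating Grade 4 with life-threatening, and the documents give no rate for such events.

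These points narrow the concern but do not remove it. Weekly discussion does not classify an event as serious and does not trigger the IRB, regulatory or company reports. The Brochure sentence leaves expected events uncovered. It also makes a site judge consistency with the Brochure before it knows whether the 24-hour duty applies, while expectedness in the table rests on a different reference.

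**Conclusion.** The point holds for one class: the expected, Brochure-consistent life-threatening event without hospitalization, disability or death. Under Section 9 as written it is not an SAE, carries no 24-hour duty to the coordinating center, and is left out of the SAE reports to the IRBs, regulatory agency and company. With Grade 4 as the stand-in, it has 10 calendar days instead of 24 hours within 30 days of the last dose. If related and later, it has no expedited deadline in the footnote.

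Two of four is a count of reporting categories, not of patients. The text does not show which of the reactions named in Section 7 count as expected, so the number of events affected cannot be estimated. The gap is narrow and softened by weekly review of each patient. It is still worth closing, because following the rule exactly misclassifies a serious event. The conclusion rests on the two readings stated with the check. The omission of the criterion from the definition does not depend on either.

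**What to change.** Add a life-threatening criterion to the numbered SAE list in Section 9, so that the definition covers the class already used in the company-reporting text.

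That alone would leave the table giving 10 calendar days for expected Grade 4 events, and the footnote silent on expected related Grade 4 events after 30 days. Reconcile both with the 24-hour SAE rule, for example by stating that the SAE notice is due first and that the table sets the deadline for the full report. State in the same edit whether Grade 4 is to be treated as life-threatening, and whether the Brochure or the agent-specific list decides expectedness.

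The cost is a few words in one section and some additional 24-hour reports. No endpoint, sample size or analysis changes.
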